- NPI (Neuropsychiatric Inventory and Stereotypic and Ritualistic Behaviors)**
- Vital signs
- Blood specimens collected (CBC, BMP, Thyroid panel, BDNF) 3 tubes total
- EKG

*Note that much of this can be filled out from past medical records

** For COVID safety or convenience, these may be completed by phone/Zoom after the visit, but completing everything during the in-person evaluation is preferred.

The breakdown between study physician and coordinator is what was agreed upon by [name] and [name], but can be renegotiated as needed depending on who is acting as physician/coordinator.

Sample schedule:

Color-codes
Coordinator
Physician
Coordinator, Physician,
Independent Evaluator

Time	Assessment
30 mins	Consent & Capacity Assessment
30 mins	Physical Exam, SCID, CSSR, CDR,
	Lawson, SAS, TESS, CGI
30 mins	MMSE, MDRS with patient
30 mins	EKG, Blood Draw with patient
45-60 mins	NPI, FBI, Zarit with Study Partner

Note that after the blood draw, samples must be dropped off at the respective labs by 3pm.

- The biomarker core lab is located on PH10-104 through the double doors in the opposite direction of the clinical rooms from the Irving reception area. There is a drop-off bin at the entrance of the lab.
- The CALM lab is located on the 15th floor of the Presbyterian Hospital in room 15-401, where there is a drop-off bin when you enter the lab.

If a patient is ineligible at a screening visit but is still interested in participating in the study, it is up to the clinical judgment of a study physician to decide whether or not to re-screen this patient. Some lab results or vital signs may change over time, making a patient eligible for the study. If a patient is re-screened and found eligible, they are no longer considered a screen fail and their status can be updated on the screening log.

Doubtful Subjects for Inclusion/Exclusion

Obtain recent labs and relevant medical records for potential research recruits whenever possible. Ideally, you will have obtained a recruit's medical records and reviewed them with a study physician prior to a screening visit. If there is any doubt that a recruit will be eligible on one or more specific criteria, study staff should do their best to obtain records and get in contact

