While study staff is to remain blinded to drug assignment (lithium/placebo) during the 12 week trial, patients will have lithium blood levels taken at weeks (2, 4,) 6, 8, and 12 for safety monitoring and dosage adjustment. We will follow the procedures successfully used for blinded lithium levels in controlled trials in mood disorders. A physician independent of the study will receive lithium levels. This unblinded physician will provide the actual lithium level to the study physician for patients randomized to lithium, and make up a comparable sham level for patients on placebo. This sham level will vary from low to high levels and will be largely based on the number of pills taken by the patient. Target serum lithium level is 0.4 - 0.6 mmol/L. Based on the blood level received and clinical response and tolerability, the study physician will adjust the number of pills at study visits.

[name] will act as the unblinded RA. At each study visit where lithium levels are drawn (weeks 2,4,6,8,12) the study coordinator will give the serum lithium/sham lithium level form to the unblinded RA with the following information already filled in: current daily dose of lithium/placebo, how administered, number of hours between last oral dose and blood draw, date blood drawn. The unblinded RA will receive lab results for patients active in the protocol, including their real lithium level results, via the CALM website. The unblinded RA will email both the partially completed serum lithium/sham lithium level form, and that patient's lab results to the unblinded physician ([name]). The unblinded physician will complete the form by writing either a real lithium level or a sham lithium level and then signing and dating the form. At this time, the unblinded physician will also enter the real lithium/sham lithium level into the updated randomization spreadsheet provided to them by the NYSPI pharmacy. The unblinded physician will email the completed form to the unblended RA, who will forward it to the study coordinator

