Upon receipt of the completed serum lithium/sham lithium levels form, the study coordinator will contact the study physician and report: the sham/real lithium level, current daily dose, and study interval. Based on this information, as well as observed tolerability and side effects, the study physician will choose to change the patient's dosage or continue with current dosage. The study coordinator will then call the patient's caregiver to inform them of the dosing change or lack thereof. The study coordinator will log all of this information on the lithium/sham level log located in the front of the patient's research chart.

If there are unusual circumstances pertaining to dosage, such as a patient having skipped a dose the day before the blood draw, provide as much relevant information as needed to the unblinded physician so they may generate the most realistic sham level. Study coordinators and physicians should instruct caregivers to avoid administering study medication to a patient the same morning of a blood draw. We are targeting trough serum lithium levels for consistent measurement. If lithium is administered the same morning as a blood draw, the serum lithium level is likely to be artificially high and exceed our target therapeutic levels for this protocol. Caregivers can be instructed to give the lithium dose after the study visit.

Breaking the Blind and Open Treatment

Once all week 12 measures are completed, the study physician will break the blind with the participant and the study partner. The unblinding information is contained in an envelope provided by the research pharmacy, which must be requested and collected prior to the week 12 visit.

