- □ If no contradictions per study clinician, instruct participant/study partner to increase dose to 450mg/day (one pill mornings, two pills evenings), using two new bottles.
- □ Schedule Week 6 visit with participant for 2 weeks after their week 2 visit.
- Obtain clinician signature on REDCap study drug issue/return log resolve any missing data from clinician forms

Week 6

Pre-visit:

Schedule an at-home blood draw via ExamOne, to occur as close to the virtual visit as possible. Notify the CALM lab of the anticipated date of this visit so they can expect the shipment. Remind study partner not to give medication dose morning of blood draw.

- □ Create zoom link & send along with date/time of visit & visit schedule to the study partner
- □ Send a calendar invitation to the study physician. In the calendar invitation, include:
 - o Zoom link
 - Links to clinician forms within REDCap for the correct subject/week
 - List of clinician forms: Treatment emergent symptoms, CGI-Severity, CGI-Change
 - Current subject medication dose, anticipated dose change after visit, & any other relevant information

During visit:

- □ Complete medication compliance check: have study partner count pills remaining in the bottle they have been using. Each bottle contains 28 pills, so calculate the number of pills that should be remaining based on dose & time since the last visit.
- On REDCap, complete the following forms with the study partner:
 - Visit registry, concomitant meds, NPI, Stereotypic/Ritualistic behaviors, study drug issue/return log

Post-visit:

- Following the at-home blood draw, complete a Serum Sham Lithium Level Form (dopamine>Lithium in FTD>Serum-Sham Lithium Levels) and send it to [name], who will send the form to [name] along with the REAL serum lithium level (once it is available on CALM). [name] will then complete the form and send it back to [name], who will send it to you. Save the signed form in a unique subject folder in dopamine>Lithium in FTD>Serum-Sham Lithium Levels.
- If no contradictions per study clinician, AND serum lithium/sham level is within the target window, instruct participant/study partner to increase dose to 600mg/day (two pills mornings, two pills evenings), using two new bottles.
- Obtain clinician signature on REDCap study drug issue/return log, resolve any missing data from clinician forms, fill out serum-sham lithium level REDCap form.

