Outcome measures and covariates. Primary outcome: agitation/aggression score (domain score on the Neuropsychiatric Inventory (NPI), continuous measure from 0-12, longitudinal); Secondary outcome: response (dichotomous, based on 30% decrease in NPI core score (sum of domains for motor activity and agitation/aggression) plus a CGI-C score of much improved or very much improved, longitudinal); Exploratory outcome motor activity score on the NPI. Covariates/Predictor variables: 1) demographic characteristics (e.g., gender, race, age); 2) baseline measures of the corresponding outcomes. Other Measures:1) tolerability, as measured by emergent side effects (TESS scores and adverse events) over the course of the 12 week trial; 2) brain derived neurotrophic factor (BDNF) serum levels.

Sample size and randomization: The randomization will be carried out by the statistician and implemented by the pharmacist, who are both otherwise independent of the research team. The randomization sequences will be balanced in blocks of random size to prevent clinicians from guessing what the next patient's treatment might be.

Modeling longitudinal data and testing hypotheses. Modeling longitudinal data and testing hypotheses. All tests will be two-sided; α =0.05; intent-to-treat with data included for all patients with ≥1 post-baseline assessment. We will use generalized linear mixed models (GLMMs; SAS PROC GLIMMIX) for longitudinal data to evaluate study aims. Models will include fixed effects for treatment group, time, group x time interaction, and any baseline covariates found to be unbalanced despite randomization. Prior to analysis, we will examine all variables at all time points for outliers and inconsistencies and examine their distributions.⁴¹⁻⁴³

Primary hypothesis: *Lithium will significantly reduce agitation/aggression as compared to placebo.*

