The following linear mixed effects model will be used: $Y_{ij} = \beta 0 + \beta 1 I T R T + \beta 2t + \beta 3t^* I T R T + \beta 4X_i + \beta 4X_i$ bi + $\epsilon i j$ where Yij is the agitation/aggression score for the *i*th subject at *t*week, *t* =0, 2,...,12, *yi0* is agitation/aggression at baseline, *liTRT* is the indicator variable for randomized condition (placebo vs. lithium), an indicator of recruitment site (Columbia University Medical Center and Johns Hopkins School of Medicine), and any baseline covariates exhibiting imbalance after randomization, bi is a random intercept to account for repeated measures across time within the patient, and $\epsilon i j$ is a random error term. Significant interaction $t^* liTRT$ indicates that the changes in agitation/aggression in each treatment group is different over time (which corresponds to rejecting the null hypothesis that β 3= 0). The effect of time will be estimated for each group separately and the groups will be compared (using contrast) at the last time point t=12. Secondary hypothesis: Lithium will have greater proportion of responders compared to placebo. We will test whether the probability of response by end of active treatment differs significantly in the lithium and placebo groups by a chi-square test. In addition, we will test whether change in the probability of response differs across treatment groups by longitudinal analysis. We will use the generalized linear mixed effects model: logit(Yij) = $\beta 0 + \beta 1$ liTRT+ $\beta 2t$ + $\beta 3t^{*}$ /*iTRT*+ $\beta 4Xi$ + *bi* + ϵij where Yij is the a binary variable indicating response for the *i*th subject at t week, t = 2, 4, ..., 12. We will first test significance of the treatment effect by testing the group by time interaction.

Exploratory Hypothesis. Lithium will significantly reduce repetitive behaviors as compared to placebo. We will use the same model in the analyses for the primary hypothesis where Yij is the motor activity score for the *i*th subject at *t* week, *t* =0, 2,...,12.

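### The coordinator who normally rates the NPI also receives, logs and enters every masked real or sham lithium level, an avoidable risk that the primary-outcome rater guesses the arm

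*Combined protocol and SAP*

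**What the plan says.** **Who rates the NPI.** The primary outcome is the "agitation/aggression score (domain score on the Neuropsychiatric Inventory (NPI), continuous measure from 0-12, longitudinal"), and in the primary model "the groups will be compared (using contrast) at the last time point t=12". Under Screening/Baseline Evaluation, the coordinator-completed list includes "NPI (Neuropsychiatric Inventory and Stereotypic and Ritualistic Behaviors"). The week 2, 6 and 10 checklists have the coordinator complete "Visit registry, concomitant meds, NPI, Stereotypic/Ritualistic behaviors, study drug issue/return log" with the study partner; weeks 4 and 8 add the Zarit interview. The week 12 checklist also gives the coordinator the NPI. The physician's form lists for weeks 2 to 10 do not contain it.

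**Where the level goes.** Under Blinding: Lithium/sham levels procedures, the unblinded physician completes the form with a real or sham value and returns it to the unblinded RA, "who will forward it to the study coordinator". The coordinator reports the value to the study physician, who decides on the dose. The coordinator then calls the caregiver, and "The study coordinator will log all of this information on the lithium/sham level log", kept at the front of the research chart. The week 6 and 8 checklists add "fill out serum-sham lithium level REDCap form", and week 12 follows the same procedure.

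**How a sham is made.** It "will be largely based on the number of pills taken by the patient". The same section also requires it to be comparable with a real level and to range from low to high.

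**The concern.** The person who normally scores the primary outcome is on the delivery route for a value that is measured in one arm and invented in the other. That person also holds most of the stated inputs to the invented value: the coordinator counts the pills and pre-fills the daily dose, the way it was given, the hours since the last dose and the draw date. A running log of values beside known doses is the setting in which values that simply track the pill count could be noticed.

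Scoring the NPI does not require the level. If it led the rater to a guess about the arm, and the guess influenced scoring, the error would move the treatment estimate itself, and no planned analysis would reveal it. The Power Analysis paragraph puts effect sizes and their 95% intervals ahead of significance tests, so a shifted estimate goes to the main result. The manual itself expects the coordinator to stay blinded even after a participant has finished.

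**Working it through.** The plan gives no figure for this point, so there is none to reproduce. The check is a trace of roles and timing, followed by an illustration on assumed inputs.

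**1. Same person.** The rater was identified from the form lists and checklists, because the colour coding of the visit tables does not survive in the text. The manual lets a physician do the screening NPI and lets the division of work be renegotiated. That creates no separation, because the study physician also receives the levels. No NPI rater without access to levels is named.

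**2. Which levels can come before which NPI.** The assay list under Biological Sample Collection has serum lithium at weeks 6, 8 and 12. Extra draws at weeks 2, 4 and 10 are possible if clinically indicated.
- Week 6: the level form is a post-visit task, so the NPI at baseline and weeks 2, 4 and normally 6 precedes any routine level.
- Weeks 6 and 8: these levels can be known before the NPI at weeks 8, 10 and 12 (week 6 level) and at weeks 10 and 12 (week 8 level).
- Week 10: there is a draw if the dose was raised at week 8 or adjustment is still needed. Its level can precede the week 12 NPI.
- Week 12: blood is drawn at the visit of the last NPI and the form is completed afterwards. This level matters only if that NPI is deferred. The checklist allows up to 3 days, and laboratory results are expected within 24 hours.

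**3. Count.** Weeks 6 and 8 for all 60 patients: 2 x 60 = 120 values at most. With the 20% attrition assumed in the Power Analysis there are 48 completers, who supply 2 x 48 = 96. The 12 dropouts supply between 0 and 24, so the range is 96 to 120.

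**4. How well could the arm be guessed? (assumed inputs)** Suppose that, given dose, real and sham levels have the same mean, that residuals are normal, and that the sham residual SD is k times the real one. Simulated best guesses with 1:1 arms are correct this often:

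| k | one level | two levels |
|---|---|---|
| 1 | 50% | 50% |
| 0.75 | 57% | 60% |
| 0.5 | 66% | 74% |
| 0.25 | 79% | 89% |

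At k = 1 the levels reveal nothing. The documents give no value of k.

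**5. What a guess could do.** Let p be the share of arms guessed correctly and d the number of points by which the rater lowers scores of patients thought to be on lithium. On average the lithium arm is lowered by p x d and the placebo arm by (1 - p) x d, so

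bias = p x d - (1 - p) x d = (2p - 1) x d.

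With d = 1 on the 0-12 scale:
- p = 0.5: 0
- p = 0.6: (1.2 - 1) x 1 = 0.2 points
- p = 0.75: (1.5 - 1) x 1 = 0.5 points

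The result is proportional to d, and it is zero if d = 0 whatever p is. For scale only: if the outcome SD were 2 to 4 points (assumed), 0.5 points would be 0.5/4 = 0.13 to 0.5/2 = 0.25 SD, against the plan's stated detectable effect of 0.58 to 0.83.

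**The case against.** The strongest case is that the procedure is already masked. The coordinator sees a number, not a label. Shams are meant to be comparable and to vary. Details such as a skipped dose are passed to the unblinded physician so that the sham is as believable as possible, which is a countermeasure and not a leak. Real levels also depend on dose, so following the pill count is not in itself a cue; it becomes one only if shams vary less than real levels, and no document says that they do. The NPI also records a caregiver's answers, which limits how far a rater's guess can move it. All of this stands, and it is why no size can be claimed.

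Some stronger readings are tempting and are not supported:
- **That the coordinator is unblinded.** The form does not mark a value as real or sham.
- **That the coordinator has no use for the level.** The week 6 and 8 checklists make the coordinator's dosing instruction depend on the level being in the target range. The level is unnecessary for rating the NPI, but the manual does give the coordinator this check, so those lines must change too.
- **That three levels per patient, or 3 x 60 = 180 values, are at stake.** The week 12 level normally arrives after the last NPI, and some patients will leave early.
- **That the coordinator sees real levels on the CALM site.** Real levels are posted there and the coordinator downloads safety results from it, but whether lithium is hidden from the coordinator's view is not stated. That is a separate question.

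It is also fair to say that the remedy is partial. The study physician, who rates the CGI used in the secondary outcome, would still see every level.

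**Conclusion.** The point holds as an avoidable exposure. The routing and the dual role are explicit; a biased result is not shown. Bias needs two things together: shams that follow the pill count more closely than real levels do, and a rater who shifts scores because of a guess. The documents support no particular value for either. The figures of 0.2 and 0.5 points are illustrations on assumed p and d, and zero is within the range. The exposure is at most about 120 routine values before a later NPI, fewer with dropout, plus any week 10 draw and, if the last NPI is deferred, the week 12 level. It is worth correcting because the change is cheap and serves the manual's own aim of a blinded coordinator.

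**What to change.** Amend Blinding: Lithium/sham levels procedures, the week 6, 8, 10 and 12 checklists, and the Research charts line that puts the log at the front of the chart:

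1. The unblinded RA sends the completed masked form to the study physician instead of the coordinator. Only the form is sent, with no laboratory results and no other communication. The coordinator still supplies the partly filled form.
2. The lithium/sham log is kept outside the chart that the coordinator uses. The unblinded RA enters the REDCap level form under restricted view.
3. The week 6 and 8 lines are reworded so that the physician confirms the existing level condition and the coordinator only relays the physician's decision to the caregiver. No dosing rule changes, and the physician still receives every level.

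**Cost.** Manual wording and a REDCap permission. The unblinded RA already handles every form, so no new role is needed, though the plan does not state that person's capacity or database access. The downsides are a little more work for the RA, loss of the coordinator's cross-check of level and log, and a direct transfer from an RA who sees real results to a blinded physician, which is why it must be limited to the form.

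**Not solved by this.** The physician rating the CGI still sees the levels. Separately, confirm what the coordinator's login to the CALM site displays.

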Medication will not be increased above 600mg/day at this visit. However, if medication adjustments are still needed, an additional blood draw for a serum lithium level may be scheduled with Exam One, with an additional blood draw kit shipped to the participant in advance, OR the participant may be scheduled to complete the visit in clinic.

The following assessments will be completed at the week 10 visit:

- Concomitant Medications
- CGI Behavior (CGI-S, CGI-C)
- CGI Global (CGI-S, CGI-C)
- NPI
- Stereotypic and ritualistic behaviors
- TESS
- Medication compliance (the study partner will be asked to count on camera the number of pills remaining in the bottle they used for the first two weeks to ensure correct dosing. 14 pills should remain in the 2nd bottle if the medication has been taken for 14 days at 450mg/day).

Completed by ExamOne (IF NECESSARY):

- Vital signs
- Serum lithium level
- Safety labs

The week 10 visit is estimated to take 50-60 minutes on average.

Color-codes	
Coordinator	
Physician	
Time	Assessment
10 minutes	TESS, Concomitant Meds, CGI, with
	Patient and Caregiver.
30 minutes	NPI with Caregiver
10 minutes	Medication compliance review

Vital signs and blood draw will be scheduled separately and completed by the Exam One mobile phlebotomy team, who will ship samples directly to the CALM lab for processing.

Week 12 Visit

At CUMC, unblinding by the study physician will occur after all week 12 measures and procedures have been completed.

The following assessments will be completed at the week 12 visit:

- Concomitant Medications
- CDR
- CGI Behavior (CGI-S, CGI-C)
- CGI Global (CGI-S, CGI-C)
- NPI
- Stereotypic and ritualistic behaviors
- TESS
- Zarit Caregiver Burden Interview
- Vital signs
- blood specimens collected
- ECG
- protocol exit form
- Medication compliance: kit collection. An additional 4 bottles (128 pills) should have been used since the week 8 visit if the bottle if the medication has been taken for 28 days at 600mg/day).

Blinding: Lithium/sham levels procedures

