The study physician will review outcome measures and results based on the first 10 weeks of the study, which will be compiled in Excel by the study coordinator before the visit (using the template "Exit Summary" excel document in dopamine>Lithium in FTD>Exit Summaries). The physician will then discuss the possibility of whether to continue the dose of lithium, if the participant was an active responder, or whether to begin a low dose of lithium if the participant was on placebo. If the study physician is not the primary physician for the participant, this decision must be discussed with the referring physician, to whom the study physician may make a recommendation. When referring to outside physicians, it is important to thoroughly inform them of the plan for lithium treatment and the target therapeutic levels for this population. The study coordinator is expected to remain blinded even after the participant completes the trial.

Adverse Events and Protocol Deviations

Adverse events and serious adverse events will be carefully monitored, recorded, and reported in this study. An adverse event (AE) is an unexpected medical occurrence or worsening of symptoms, which does not necessarily have a causal relationship with study treatment. Study physicians should monitor gait disturbances or tremor of at least moderate intensity as well as falls in particular for this study. A serious adverse event (SAE) is a medically serious event, any event requiring hospitalization, and death.

Each patient that has an AE or SAE reported will have an AE log filed in their research chart. Both AE and SAE are to be recorded on the AE log version date 07/18/2016. AE logs are to-data forms for this study. Hardcopy AE forms are rewritten each time new information about the event is

made available, with all revisions kept in paper research charts. However, the database AE form will only contain information reflecting the final resolved event or last recorded information once the patient has left the protocol. Information regarding the treatment provided, outcome, and presumed relationship to study drug will be updated as new information becomes available. Site PIs will sign the bottom of the AE logs for their own site once the patient has exited the protocol.

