- Schedule visit with participant for 2 weeks after they receive the study drug kit. During this call, also confirm dosing schedule (1 pill in evenings) and ask them to use the same bottle during the 2 week period.
- □ Create zoom link & send along with date/time of visit & visit schedule to the study partner
- Send a calendar invitation to the study physician. In the calendar invitation, include:
 - o Zoom link
 - Links to clinician forms within REDCap for the correct subject/week
 - o List of clinician forms: Treatment emergent symptoms, CGI-Severity, CGI-Change
 - Current subject medication dose, anticipated dose change after visit, & any other relevant information

During visit:

- □ Complete medication compliance check: have study partner count pills remaining in the bottle they have been using. Each bottle contains 28 pills, so calculate the number of pills that should be remaining (14 if 2 weeks from kit receipt)
- On REDCap, complete the following forms with the study partner:
 - Visit registry, concomitant meds, NPI, Stereotypic/Ritualistic behaviors, study drug issue/return log

Post-visit:

- □ If no contradictions per study clinician, instruct participant/study partner to increase dose to 300mg/day (one pill mornings, one pill evenings), using a new bottle.
- □ Schedule Week 4 visit with participant for 2 weeks after their week 2 visit.
- Obtain clinician signature on REDCap study drug issue/return log, resolve any missing data from clinician forms

Week 4

Pre-visit:

- □ Create zoom link & send along with date/time of visit & visit schedule to the study partner
- Send a calendar invitation to the study physician. In the calendar invitation, include:
 - o Zoom link
 - o Links to clinician forms within REDCap for the correct subject/week
 - List of clinician forms: Treatment emergent symptoms, CGI-Severity, CGI-Change, Simpson-Angus, Lawton, CDR
 - Current subject medication dose, anticipated dose change after visit, & any other relevant information

During visit:

- □ Complete medication compliance check: have study partner count pills remaining in the bottle they have been using. There should be 0 remaining if 14 days have passed since the previous visit (and they were taking 2 pills daily).
- □ On REDCap, complete the following forms with the study partner:
 - Visit registry, concomitant meds, NPI, Stereotypic/Ritualistic behaviors, Zarit Burden Interview, study drug issue/return log

Post-visit:

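### The physician who rates CGI and TESS is unblinded participant by participant during accrual, which weakens the masking of later participants' ratings, most of all at week 12

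*Combined protocol and SAP*

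**What the plan says.** - **Timing of unblinding.** The section Breaking the Blind and Open Treatment sets the rule: "Once all week 12 measures are completed, the study physician will break the blind with the participant and the study partner". The Week 12 Visit section agrees: "At CUMC, unblinding by the study physician will occur after all week 12 measures and procedures have been completed". Nothing defers this until accrual or rating has ended.
- **Who rates.** Screening/Baseline Evaluation lists CGI and TESS as physician-completed. The Week 2 checklist has: "List of clinician forms: Treatment emergent symptoms, CGI-Severity, CGI-Change". Weeks 4 to 10 list the same forms for the clinician. The week 12 checklist does not itemise the clinician's forms, but CGI and TESS are week 12 assessments and no other rater is named.
- **Who doses.** Blinding: Lithium/sham levels procedures: "the study physician will choose to change the patient's dosage or continue with current dosage".
- **Who stays blind.** The same section opens: "While study staff is to remain blinded to drug assignment (lithium/placebo) during the 12 week trial". After exit, the rule covers one role only: "The study coordinator is expected to remain blinded even after the participant completes the trial". The week 12 checklist also has the research assistant leave before the clinician's part of the visit.
- **Stated protection.** Sample size and randomization: "The randomization sequences will be balanced in blocks of random size to prevent clinicians from guessing what the next patient's treatment might be". Block sizes are not given.

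**The concern.** Enrolment is one participant at a time and each course lasts 12 weeks. When one participant reaches week 12, earlier participants have normally finished and had their envelopes opened by the physician who is about to rate. That physician can gain information in two ways.

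1. **Running count.** Blocks end balanced, so if more lithium than placebo has been revealed so far, placebo is the better guess for the next person on the list. Research charts says drug IDs are issued chronologically, so the order is visible.
2. **Case-by-case learning.** At each exit the physician reviews an outcome summary with the assignment known. Over time this shows which side effects and which reported levels went with which arm. Random block sizes do not bear on this.

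Two planned analyses use the exposed ratings. The responder outcome requires a CGI-C of much or very much improved. The tolerability t-test compares TESS change from baseline to week 12. The Introduction also names the CGI among the primary outcome measures, although the statistical section makes NPI agitation/aggression the only primary outcome.

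**Working it through.** The documents give no figure for predictability, so there is none to reproduce. The question is how often a guess of arm would be right.

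**Inputs from the documents:** 60 participants allocated 1:1 and 20% planned attrition (Power Analysis); 12-week course; blocks of random size; two recruitment sites in the primary model.

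**Assumptions:** block-size sets {2,4}, {2,4,6}, {4,6} and {4,6,8}; accrual spread evenly over 2 to 5 years; at the upper end, one list, one physician and completion in enrolment order.

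**Rule:** guess the arm with the smaller revealed count, and toss a coin if the counts are equal. Then

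P(correct) = P(unequal) × P(correct given unequal) + P(equal) × 0.5.

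At a participant's own week-12 rating, with every earlier assignment revealed, simulation gives:

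- {2,4}: counts unequal for 55%, guess then right 90%: 0.55 × 0.90 + 0.45 × 0.5 = 0.72
- {4,6,8}: counts unequal for 64%, guess then right 78%: 0.64 × 0.78 + 0.36 × 0.5 = 0.68

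A second method, which updates the probabilities over the unknown position within a block, gives nearly the same figures. Its results by number of most recent earlier participants still blinded are:

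| Block sizes | none (own week 12) | 1 | 2 | 3 |
|---|---|---|---|---|
| {2,4} | 72% | 55% | 53% | 50% |
| {2,4,6} | 70% | 58% | 55% | 52% |
| {4,6} | 69% | 59% | 56% | 52% |
| {4,6,8} | 68% | 60% | 56% | 53% |

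**At enrolment.** With 60 participants over 5 or 2 years, on average 2.7 or 6.5 earlier participants are still blinded. With 1 to 3 still blinded the guess is right about 50-60% of the time; with 6, 50%. Certain prediction occurs in under 1% of allocations once 2 or more are still blinded.

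**At dose decisions.** With the running-count rule, {2,4} and {4,6,8} blocks and 2 to 5 years of accrual, the guess is right 50-60% of the time at weeks 2 to 6 and 54-62% at week 8, even if every earlier assignment is eventually revealed.

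**Sensitivity of the week-12 figure** (running-count rule, all four block sets):

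- every earlier assignment revealed: 68-72%
- a random 20% never revealed: 57-58%
- one list shared equally by two sites, with only own-site assignments seen: about 54%
- both: about 53%

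Even at the upper end, certainty at week 12 is rare: 11%, 4%, 5% and 2% for the four sets in table order.

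The case-by-case route cannot be quantified from the documents.

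**The case against.** A reader might infer that allocation becomes predictable and that the random-block safeguard fails. The documents do not support that. The safeguard is aimed at the next patient's treatment, and at enrolment the guess stays at about 50-60% or lower. Nor does the manual let a participant's own assignment be opened before that participant's ratings; the order is explicit.

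The 68-72% is a best case for the guesser. The manual sends early exits through the week 12 measures and procedures but does not say that their envelopes are opened. The Week 12 unblinding rule refers to one site while the model names two, and whether each site has its own list is not stated. These objections stand and are why the range reaches down to 53%. They do not remove the point: a guesser more sophisticated than the running-count rule could do better in those scenarios, and if early exits are unblinded and each site has its own list, the higher figures apply.

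A reader might also infer that dosing is exposed to the same degree. It is not: titration falls at weeks 2 to 8, where the count says little.

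The primary outcome is well placed. Follow-up NPI is on the coordinator's checklist and the coordinator stays blind. A responder also needs a 30% fall in the NPI core score, so CGI-C alone cannot create one. Sham levels are meant to be comparable and to vary, which limits what levels reveal, and the study is a pilot focused on effect sizes. All of this limits the damage, but none of it masks the CGI-C and TESS rater.

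**Conclusion.** The point holds as a cheap improvement, with medium confidence. The plan protects the coordinator's blind after exit but not that of the physician who rates CGI and TESS, so masking of those ratings weakens as participants finish. At the week-12 rating the arm could be guessed correctly in about 53-72% of participants from the allocation count alone, against 50% under full masking. Where the truth lies depends on block sizes, whether early exits are unblinded, the number of lists and the number of physicians; none of these is stated. Before week 12 the guess also depends on accrual time. How far a better-than-chance guess would shift CGI-C or TESS scores cannot be derived from the documents. Dose decisions are only slightly exposed through the count, and the coordinator-rated NPI primary outcome is not directly affected.

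**What to change.** Amend Week 12 Visit, Breaking the Blind and Open Treatment, and the week 12 checklist as follows.

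- Have the envelope opened and the assignment disclosed by someone who rates no active participant: the existing unblinded physician, who already receives the randomization tables, or the treating or referring physician.
- Take the envelope out of the clinician's rating folder.
- Keep the CGI/TESS rater blind until the last participant's week-12 ratings are entered.
- Where the rater must be told for clinical care, log the date so that later ratings can be identified.
- Report a coordinator-rated response (30% fall in the NPI core score alone) beside the composite response.

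With the rater kept blind, the allocation count carries no information and the guess returns to 50%. The cost is a change to the manual and a handover at exit, using roles that already exist. It is less convenient where the study physician is also the treating clinician.
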